7.2. Safety Assessments

Planned time points for all safety assessments are provided in the Tables 2 to 4. Unscheduled clinical laboratory measurements may be obtained at any time during the study to assess any perceived safety concerns.

7.2.1. Physical examinations

A complete physical examination will include, at a minimum, assessments of the cardiovascular, respiratory, gastrointestinal, and neurological systems.

A complete physical examination will be performed at the screening visit.

A targeted physical examination will be performed only when needed to evaluate possible adverse event (s) (i.e. any new signs or symptoms). No routine physical exam is needed for study visits after Day 1.

7.2.2. Vital signs

Vital signs will be measured as specified in the Tables 2 to 4 and as clinically indicated. Vital signs will be measured with the participant in a semi-supine position after 5 minutes of rest and will include:

- Body temperature
- Pulse rate
- Systolic and diastolic blood pressure
- Respiratory rate

Additional vital signs may be measured during the study if warranted, as determined by the investigator.

7.2.3. Electrocardiograms

12-Lead ECGs should be collected at times specified in the Tables 3 and 4 using an ECG machine that automatically calculates the heart rate and measures PR interval, QT interval, and QTc intervals and QRS time limit. All scheduled ECGs should be performed after the participant has rested quietly for at least 10 minutes in a supine position. Generally, ECGs should not be collected within 3 hours after food or beverage consumption.

QTcB and QTcF will be analyzed in SAP.

If a postdose QTc interval remains 30 msec from the baseline and is >450 msec; or an absolute QTc value is 500 msec for any scheduled ECG for greater than 4 hours (or sooner, at the discretion of the investigator), or QTc intervals get progressively longer, the participant should undergo continuous ECG monitoring. A cardiologist should be consulted if QTc intervals do not return to less than the criterion listed above after 8 hours of monitoring (or sooner, at the discretion of the investigator).

In some cases, it may be appropriate to repeat abnormal ECGs to rule out improper lead placement as contributing to the ECG abnormality. It is important that leads be placed in the same positions each time in order to achieve precise ECG recordings. If a machine read QTc value is prolonged,

as defined above, repeat measurements may not be necessary if a qualified medical provider's interpretation determines that the QTc values are in the acceptable range.

ECG will be in digital format and be read locally.

7.2.4. SpO₂

Record SpO₂ while participant is at rest, at the same time record oxygen supplementation: low flow oxygen, high flow oxygen, or other. Record FiO₂ if known, and method of delivery, if applicable.

7.2.5. Clinical Safety Laboratory Assessments

Fasting is not required before collection of laboratory samples; Day 1 clinical laboratory tests are performed prior to infusion as a baseline.

Blood will be collected at the time points indicated in the Tables 2 to 4. Testing items including:

- Hematology: Red blood cell count; hemoglobin concentration; platelet count; white blood cell count; absolute value and percentage of: lymphocytes, monocytes, neutrophils, eosinophils, basophils;
- Urinalysis: Urine occult blood, urine bilirubin, urobilinogen, urine ketone body, urine protein, urine nitrite, urine glucose, urine pH, urine specific gravity, urine white blood cells, urine white blood cells (high power field), urine red blood cells, and urine red blood cells (high power field);
- Serum chemistry: AST, ALT, total bilirubin, direct bilirubin, indirect bilirubin, total protein, alkaline phosphatase, glutamyl transpeptidase, urea, blood creatinine, albumin, creatine kinase, C-reactive protein, blood glucose, potassium, and sodium, chlorine, lactate dehydrogenase (LDH);
- Coagulation test: Prothrombin time, activated partial thromboplastin time, fibrinogen;
- IL-6; Ferritin; Procalcitonin; Thrombin time; D-dimer.

The investigator must review the laboratory report, document this review, and record any clinically relevant changes occurring during the study in the AE section of the CRF. Clinically significant abnormal laboratory findings are those which are not associated with the underlying disease, unless judged by the investigator to be more severe than expected for the participant's condition.

All laboratory tests with values considered clinically significantly abnormal during participation in the study should be repeated until the values return to normal or baseline or are no longer considered clinically significant by the investigator or medical monitor.

If such values do not return to normal/baseline within a period of time judged reasonable by the investigator, the etiology should be identified and the sponsor notified.

All protocol required laboratory assessments must be conducted in accordance with the laboratory manual.

If laboratory values from non-protocol specified laboratory assessments performed at the institution's local laboratory require a change in participant management or are considered

clinically significant by the investigator (e.g., SAE or AE or dose modification), then the results must be recorded in the CRF.

7.2.6. ADE Assessments

Monitor for new infections and adverse events until 120 days (if discharged, via biweekly telephone visit, in-person or virtual visit).

7.2.7. Pregnancy Testing

Pregnancy tests are serum tests, but must have a sensitivity of at least 25 mIU/mL. Women of childbearing potential (WOCBP) must undergo pregnancy testing according to the Tables 2 to 4. Following a negative pregnancy test result at screening, appropriate contraception must be commenced. Pregnancy tests will also be done whenever 1 menstrual cycle is missed during the study (or when potential pregnancy is otherwise suspected) and at the end of the study. Pregnancy tests may also be repeated if requested by institutional review boards (IRBs)/ethics committees (ECs) or if required by local regulations.

Participants who are pregnant will be discontinued from the study.

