4.2. Exclusion Criteria

1. Hospitalized patients who need non-invasive ventilation or high flow oxygen (i.e., 6 point on the 8-point ordinal scale);
2. Patients with critical COVID-19. According to the NIH definition, critical patients are those individuals who have one of the following: 1) respiratory failure and need invasive mechanical ventilation; 2) septic shock; 3) multiple organ dysfunction;
3. Patients with severe COVID-19 who received convalescent plasma or anti-SARS-CoV-2 S protein targeted therapy;
4. ALT or AST is 5 times higher than the upper limit normal range;
5. $\text{eGFR} < 30 \text{ mL/min}$ or on dialysis {eGFR calculated by Cockcroft-Gault formula (*Cockcroft DW, 1976*), Male: $\text{CrCL} (\text{mL/min}) = [(140 - \text{age}) \times \text{weight} (\text{kg})] \times 1/[\text{SCr}]$ }

(mg/dL) \times 72]; Female: CrCL (mL/min) = [(140 - age) \times weight (kg)] \times 0.85 / [SCr (mg/dL) \times 72] };

6. Pregnant or lactating women;
7. Anticipated discharge from the hospital or transfer to another hospital which is not a study site within 72 hours;
8. A patient who is allergic to the active ingredients or components of SCTA01;
9. Patients participated in other clinical studies related to COVID-19 or SARS-CoV-2 infection within 30 days before enrollment or five half-lives of investigational product, whichever is longer.

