5.2. Administration

Each participant will receive a single intravenous infusion of either SCTA01 or placebo. Infusion volume will be 500 mL and infusion time is 3 hours (\pm 0 minutes).

Phase II part of the study: Subjects will receive a single dose of SCTA01 (15 mg/kg), SCTA01 (50 mg/kg), or placebo within 24 hours after randomization.

Phase III part of the study: Subjects will receive a single dose of SCTA01 (X mg/kg or X mg) or placebo within 24 hours after randomization.

Further instruction on the preparation and administration of the investigational product will be provided to the site in Pharmacy Manual.

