Urinalysis		X		X		X		X		X	
Serum chemistry		X		X		X		X		X	
Coagulation test		X		X		X		X		X	
IL-6		X		X		X		X		X	
Ferritin		X		X		X		X		X	
Procalcitonin		X		X		X		X		X	
Thrombin time		X		X		X		X		X	
D-dimer		X		X		X		X		X	
Immunogenicity blood samples							X		X	X	

PK samples				X ^{1,2}	X ¹	X ^{1,2}			X ^{1,2}		1: Intensive sampling of Phase II part: Blood samples will be collected in the same 30 subjects as the Table 3. 2. Sparse sampling of Phase II part: Blood samples will be collected in the remaining subjects (excluding the 30 subjects with intensive PK sampling) of each group of Phase II part.
Blood for SARS-CoV-2 test	X		X		X	X		X	X		Only performed while patient is in hospital or attends an in-person visit.
NP or OP swab for SARS-CoV-2 test	X	X	X	X	X	X		X	X		Continue testing at the scheduled time-point while hospitalized or attends an in-person visit, until the NP or OP swab samples viral RNA test is negative. NP swab preferred. If NP swab can't be obtained, OP swab may be used.
Sequencing the gene encoding spike protein		Will be tested in subjects who do not achieve a reduction in viral shedding or persistence viral presence or have a rebound in viral shedding following suppression									Using reserved NP or OP swab samples. No additional sampling is required.
8-Point Ordinal Scale	Daily until discharge			X	X	X			X		Only performed while patient is in hospital or attends an in-person visit, otherwise performed by phone call to assess clinical status (ordinal scale). The date and cause of discharge or re-hospitalization after discharge should be recorded.

Concomitant medications		Daily until discharge	
SpO ₂		Daily until discharge	Report the best reading if multiple readings are obtained in a day. Also record oxygen supplementation: low flow oxygen, high flow oxygen, or other.
AEs		Daily until discharge and biweekly via phone call after discharge until 120 days.	
ADE		Monitor for new infections and adverse events until 120 days (if discharged, via biweekly telephone call, in-person or virtual visit).	

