8. ADVERSE EVENTS

8.1. Monitoring, Recording, and Reporting of Adverse Events

An adverse event (AE) is any unfavorable and unintended sign (including an abnormal laboratory finding, for example), symptom, or disease temporally associated with the use of a medicinal product, whether or not considered related to the medicinal product. It may be a new intercurrent illness, a worsening concomitant illness, an injury, or any concomitant impairment of the subject's health, including laboratory test values, regardless of etiology. Any worsening (i.e., any clinically significant adverse change in the frequency or intensity of a pre-existing condition other than disease under study) should be considered as an AE. A diagnosis or syndrome should be recorded on the AE page of the CRF rather than the individual signs or symptoms of the diagnosis or syndrome.

The signs/symptoms/clinical sequelae resulting from COVID-19 are not considered as AEs. The deaths resulting from COVID-19 that are consistent with the clinical endpoint definition should not be recorded as AEs. These data will be captured as efficacy assessment data on the relevant pages of the CRF, as they are expected endpoints.

AEs may also include pre-treatment or post-treatment complications that occur as a result of protocol specified procedures, lack of efficacy, overdose, drug abuse/misuse reports, or occupational exposure. Pre-existing events that increase in severity or change in nature during or as a consequence of participation in the clinical study will also be considered as AEs. All AEs will be recorded by the investigator from the time the subject signs the ICF through Day 120 after the last dose of the study drug or until the last study visit, whichever is longer. AEs and SAEs will be recorded on the AE page of the CRF and in the subject's source documents. All SAEs must be reported to Drug Safety of SCT within 24 hours of the investigator's knowledge of the event. Refer to Sections 8.5 and 8.6 for SAE reporting details.

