8.2.6. Outcome

The Investigator will report the outcome of the event for both AEs and SAEs. Non-serious AEs will be followed for 120 days after the subject's last dose of the study drug. All SAEs that have not resolved upon discontinuation of the subject's participation in the study must be followed until recovered, recovered with sequelae, not recovered (death due to other cause), and death (due to the SAE), lost to follow up, or otherwise explained.

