8.5. Reporting Serious Adverse Events

Any AE that meets the criteria for an SAE requires the completion of an ICSR Form in addition to being recorded on the AE page of the CRF. All SAEs must be reported to Drug Safety Department of SCT and CRO within 24 hours of the Investigator's knowledge of the event using the Individual Case Safety Report (ICSR) Form by sending email to the safety mailbox of CRO ([contact]) and copying to Drug Safety of SCT ([contact]). This instruction pertains to initial SAE reports as well as any follow-up reports.

The investigator is required to ensure that the data on these forms are accurate and consistent. This requirement applies to all SAEs (regardless of relationship to the study drug) that occur during the

study (from the time the subject signs informed consent to Day 120 after the last dose of the study drug), and those made known to the investigator at any time thereafter that are suspected of being related to the study drug. AEs/SAEs occurring prior to treatment will be captured.

The SAE report should provide a detailed description of the SAE and include summaries of hospital records and other relevant documents. If a subject died and an autopsy has been performed, copies of the autopsy report and death certificate are to be sent to Drug Safety of SCT as soon as these become available. Any follow-up data will have to be detailed in a subsequent ICSR Form and sent to Drug Safety of SCT.

Where required by local legislation, the investigator is responsible for informing the IRB or independent ethics committee (IEC) of the SAE and providing them with all relevant initial and follow-up information about the event. The Investigator must keep copies of all SAE information on file including correspondence with CRO and the IRB/IEC.

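### Section 7.2.7 takes pregnant participants out of the study even after the single infusion, which ends the scheduled contacts to Day 120 that other sections rely on to find new adverse events and antibody-dependent enhancement

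*Combined protocol and SAP*

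**What the plan says.** Section 7.2.7 requires a negative test at screening, then further tests when a menstrual cycle is missed, when pregnancy is suspected, and at the end of the study. It closes with: "Participants who are pregnant will be discontinued from the study". It makes no distinction between before and after infusion and has no provision for safety follow-up.

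Entry and dosing are set elsewhere. Section 4.2 excludes "Pregnant or lactating women". Section 5.2 says: "Each participant will receive a single intravenous infusion of either SCTA01 or placebo", within 24 hours of randomization.

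Safety follow-up is set by time since dose:

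- Table 4, AE contacts: "Daily until discharge and biweekly via phone call after discharge until 120 days".
- Section 7.2.6, ADE: "Monitor for new infections and adverse events until 120 days (if discharged, via biweekly telephone visit, in-person or virtual visit".
- Section 8.1: "All AEs will be recorded by the investigator from the time the subject signs the ICF through Day 120 after the last dose". The sentence goes on to offer the last study visit as the alternative end point and to apply the later of the two.
- Section 8.2.6: "Non-serious AEs will be followed for 120 days after the subject's last dose of the study drug".
- Section 8.5, SAEs: "from the time the subject signs informed consent to Day 120 after the last dose of the study drug".

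Section 6.1 keeps a participant in follow-up when study treatment is stopped for good. Section 8.4 requires pregnancies after the start of study medication to be reported, with monitoring and care until the outcome.

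**The concern.** Stopping a drug when pregnancy is found is normal, but here the only dose has nearly always been given by then. Removal from the study protects the woman from no further exposure, and it ends the planned observation of an exposure that has already happened.

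The protocol set 120 days of AE and ADE contact for everyone. Section 2.9, Table 1 reports mean half-lives in healthy volunteers of 574 to 1040 hours (574/24 = 23.9 days; 1040/24 = 43.3 days), so the antibody persists for weeks. A site that applies 7.2.7 literally stops the contacts; a site that gives priority to Section 8 may keep them. The intensity of safety follow-up in women exposed around or during pregnancy would then depend on which section a site puts first.

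**Working it through.** There is no figure in the plan to reproduce. The check sets the sections side by side.

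1. **Whom the rule reaches.** A positive screening test already bars entry under 4.2. Table 2 puts the pregnancy test in the screening period (Day -3 to Day -1). Table 3 (Day 1) lists no pregnancy test. Table 4 tests only on suspicion and at the end of the study. With infusion due within 24 hours of randomization, the triggers that 7.2.7 adds after screening fall almost entirely after the single dose.

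2. **What the rule ends.** Its object is the study, not the drug. The protocol treats these as different things: 6.1 covers stopping treatment and retains the participant, and 6.3 ties the end of outcome collection to withdrawn consent. Pregnancy after dosing is neither. Taken as worded, 7.2.7 therefore ends the remaining Table 4 visits, the AE and ADE contacts to Day 120, and ordinal scoring if the pregnancy is found before Day 29. In that last case, 9.7.1 would presumably treat the woman as terminated early for a reason other than an AE and censor her at her last assessment.

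3. **What survives.** For a dosed woman who leaves on day t < 120, the AE window in 8.1 is the later of Day 120 after dose and the last visit: max(120, t) = 120. Recording therefore remains due to Day 120. Section 8.5 likewise keeps SAE reporting to Day 120, and beyond it for SAEs suspected to be drug-related that become known to the investigator. Section 8.2.6 follows SAEs still open at discontinuation. Section 8.4 covers pregnancy outcome and SAEs that are adverse pregnancy outcomes, including after the study. Sections 7.4.1, 7.6 and 7.7 provide swab, PK (Phase II) and anti-drug antibody samples at early withdrawal.

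4. **What does not survive.** The scheduled contacts between t and Day 120 are the planned means of learning about new events. The surviving clauses require events to be recorded or reported, follow events already known, concern the pregnancy itself, or provide a single assessment at exit. None expressly continues the AE and ADE contacts.

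5. **Result.** The duty to collect runs to Day 120, while the contact schedule that serves it stops at t. The unscheduled interval is 120 - t days. The documents give no distribution for t and no expected number of pregnancies.

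**The case against.** The strongest reply is that the sections can be read together: routine participation ends, the early-withdrawal assessments are done, and AE, SAE and pregnancy follow-up continue under Section 8. The later-of-two wording in 8.1 points to Day 120 collection even when visits end early, and 6.3 gives no reason to stop collecting outcomes from a woman who still consents. Section 8.6 also refers sites to completion guidelines for the pregnancy report form, which are not available here and may say more.

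Much of this stands. A reader might infer that 7.2.7 cancels AE and SAE collection for these women, or that their safety data are lost altogether. The documents do not support that: the recording duty survives under 8.1 and 8.5, open SAEs are followed, and pregnancy outcomes are reported. A reader might also want to count the contacts lost. The documents do not support a count either: the day of detection would have to be assumed, biweekly has two meanings, and Table 4 starts the calls at discharge, not at detection.

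What does not stand is the claim that reading the sections together closes the gap. That reading keeps the duty but has to supply the contacts itself, and it must set the plain words of 7.2.7 aside to do so.

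**Conclusion.** The point holds as an internal conflict with a limited safety consequence. For women found pregnant after infusion, 7.2.7 as worded removes the scheduled contact through which new AEs and ADE would be found. That conflicts with the Day 120 windows in 8.1, 8.2.6 and 8.5 and is out of line with 6.1.

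The size is small. Entry needs a negative test, and 4.1 requires abstinence or effective contraception, so few women should be affected. Any effect on the primary endpoint is confined to pregnancies found before Day 29 and would not change the efficacy conclusion. The point rests on reading 7.2.7 literally, and on no unseen site instruction overriding it. It is a cheap improvement, not a threat to the trial.

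**What to change.** Amend 7.2.7 to state two cases:

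- Participants found pregnant before infusion are not dosed and are discontinued.
- Participants found pregnant after infusion remain, with consent, in scheduled safety and outcome follow-up to Day 120, by phone where suitable. Any procedure contraindicated in pregnancy is omitted. They are also followed to pregnancy outcome under 8.4.

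The cost is one or two sentences in the next amendment; the visits, calls and forms already exist. The downside is continued contacts and some blood draws for a few pregnant women. Consent and the telephone option in 7.2.6 keep that burden low.

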7.3. Clinical Efficacy Assessments

For all baseline assessments and follow-up visits, refer to the Tables 3 and 4 for procedure to be done, and details below for each assessment.

7.3.1. Time to Clinical Improvement

The subject's clinical status will be evaluated using the 8-point ordinal scale every day until Day 29 while being hospitalized. However, if the subject is discharged from the hospital before Day 15, Day 22, or Day 29, he/she only needs to come back to the hospital on Day 15, Day 22, and/or Day 29 for evaluation along with completing other procedures. If the discharged subject is unable to return for visits on these days, the evaluation can be done over the [contact]-Point Ordinal Scale

The ordinal scale is the primary measure of clinical outcome. The scale used in this study is as follows (from worst to best):

- 8: Death;
- 7: Hospitalized, on invasive mechanical ventilation or ECMO;
- 6: Hospitalized, on non-invasive ventilation or high flow oxygen devices;
- 5: Hospitalized, requiring supplemental oxygen;
- 4: Hospitalized, not requiring supplemental oxygen - requiring ongoing medical care (COVID-19 related or otherwise);
- 3: Hospitalized, not requiring supplemental oxygen - no longer requires ongoing medical care;
 - This would include those kept in hospital for quarantine/infection control, awaiting bed in rehabilitation facility or homecare, etc.;
- 2: Not hospitalized, limitation on activities and/or requiring home oxygen;
- 1: Not hospitalized, no limitations on activities.

To determine a subject's clinical status using the ordinal scale, the investigator should:

On Day 1, report their clinical status at randomization; On Day 2, report the clinical status from randomization to midnight on Day 1; On Day 3 through Day14 or until discharged and On Days 15, 22 and 29, provide the worst clinical assessment for the previous day [i.e., midnight to midnight; 00:00 ~ 23:59 (24-hr clock)]. For example, on Day 3 when completing the form, the worse clinical outcome measure of Day 2 is captured with the worst being death followed by ECMO, mechanical ventilation, etc. The Day 2 measurement is assessed as occurring anytime in that 24-hour period (00:00 ~ 23:59).

